### **3 INTRODUCTION**

This statistical analysis plan (SAP) for the final analysis is based on the most recent approved clinical study protocol (CSP), the most recent approved electronic case report form (eCRF), and the most recent approved eCRF completion guidelines.

This SAP (Methods) documents the planned statistical analyses of safety and other endpoints.

The SAP (Methods) will be finalized and approved prior to the clinical database lock for the final analysis. Analyses will be performed separately for Part A and B, unless otherwise specified. Any revisions to the approved SAP will be documented and approved in an amendment to the SAP prior to the clinical database lock for the final analysis. Any changes made to the SAP Methods after the clinical database lock has occurred will be documented in the clinical study report for this study.

The Vertex Biometrics Department will perform the statistical analysis described in this document. SAS (Version 9.4 or higher) will be used to generate all statistical outputs (tables, figures, listings, and datasets).

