### **6 STUDY DESIGN**

#### **6.1 Overall Design**

This is a Phase 3, multicenter, open-label study for subjects who transferred from Study 659-105, a Phase 3 Vertex study investigating VX-659/ TEZ/IVA, who meet eligibility criteria (Section 8 in CSP).

[figure not shown]
Two separated regional amendments were developed in March 2021. The regional protocol for US and UK was amended to add optional home collected sweat chloride at unscheduled home visit. The study design kept intact as the original one-part design. The regional protocol for Australia, Canada, Spain and Poland was amended to add a Part B, so that subjects in these countries without commercially-available ELX/TEZ/IVA who complete Part A would have the opportunity to participate in Part B for an additional 48 weeks.

A schematic of the study design for the regional amendment of Australia, Canada, Spain and Poland is shown in Figure 6-1. The schematic of the study design for other countries contains only Part A of the Figure 6-1.

All subjects in Parts A and B will receive a TC of ELX/TEZ/IVA at the same dose level as that evaluated in the ELX Phase 3 pivotal trials (ELX 200 mg once daily [qd], TEZ 100 mg once daily [qd], and IVA 150 mg every 12 hours [q12h]). Study drug administration is described in Section 9.6 in CSP.

Study visits and assessments to be conducted for Parts A and B are shown in Table 3-1 and table 3-2, of the CSP respectively. All visits will occur within the windows specified.

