## **8 STATISTICAL ANALYSIS**

### **8.1 General Considerations**

In general, data will be summarized by the treatment group in this study.

The precision standards for reporting safety variables are provided in an internal Biometrics document that specifies the programming rules including the precision for derived variables.

**Continuous variables** will be summarized using the following descriptive summary statistics: the number of subjects (n), mean, standard deviation (SD), median, minimum value (min), and maximum value (max).

**Categorical variables** will be summarized using counts and percentages. Percentages will be presented to 1 decimal place.

**Baseline value**, unless otherwise specified, for the long-term safety analysis is defined as the most recent non-missing measurement (scheduled or unscheduled) collected before the first dose of ELX/TEZ/IVA in Part A of this study.

Baseline of sweat chloride is defined as the most recent non-missing sweat chloride (scheduled or unscheduled) collected before the first dose of VX-659 in VX17-659-102 or VX17-659-103 studies.

**Absolute change** from baseline will be calculated as post-baseline value - baseline value.

**Relative change** from baseline will be calculated as  $100\% \times (\text{post-baseline value} - \text{baseline value}) / \text{baseline value}$ .

**Treatment-emergent (TE) Period** for Part A will include the time from the first dose of study drug in Part A to 28 days after the last dose date of the study drug in Part A or to the completion date of study participation in Part A (Section 9.1.5 of the CSP), whichever occurs first.

**Treatment-emergent (TE) Period** for Part B will include the time from the first dose of study drug in Part B to 28 days after the last dose date of the study drug in Part B or to the completion date of study participation in Part B (Section 9.1.5 of the CSP), whichever occurs first.

The completion date of study participation will be obtained from the end of study page of the eCRF for each part respectively.

For subjects who participate in another qualified Vertex study before completing Study VX18-445-113 and resume participation in Study VX18-445-113, the TE Period for either Part A or B will exclude the time spent in the other study.

**Unscheduled visits:** Unscheduled visit measurements will be included in analysis as follows:

- 1) In scheduled visit windows per specified visit windowing rules

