### **8.2.5 Study Drug Exposure**

Exposure summaries will be separated for Parts A and B based on the Safety Set.

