### **8.4 Safety Analysis**

The primary objective of the study is the evaluation of the long-term safety and tolerability of ELX/TEZ/IVA. Safety analysis will be summarized separately for Parts A and B. Part A safety analyses will be based on the TE Period for Part A for subjects in the Safety Set for Part A. Part B safety analyses will be based on the TE Period for Part B for subjects in the Safety Set for Part B. The overall long-term safety profile of study drug will be assessed in terms of the following safety and tolerability endpoints:

- Treatment-emergent adverse events (TEAEs)
- Clinical laboratory values (i.e., serum chemistry, hematology, coagulation, and urinalysis)
- ECGs
- Vital signs including body weight and BMI
- Pulse oximetry
- Spirometry

Only descriptive analysis of safety will be performed, and no statistical testing will be performed.

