#### **8.4.1 Adverse Events**

Summaries of TEAEs will be provided separately for Parts A and B based on the Safety Set.

For analysis purposes, AEs will be classified as pretreatment AEs, TEAEs, or post-treatment AEs for the corresponding part, defined as follows:

- **Pretreatment AE:** any AE that occurred before the first dose date of study drug in the TE Period in the corresponding part. For subjects who enroll in another qualified Vertex study before completing this study and resume participation in this study, AEs that started during participation in another qualified Vertex study and are ongoing at the time of Returning Visit will be flagged as pre-treatment AE.

- **TEAE:** any AE that worsened (either in severity or seriousness) or newly developed at or after the first dose date of study drug in the TE Period in the corresponding part.
- **Post-treatment AE:** any AE that worsened (either in severity or seriousness) or that was newly developed after the TE period in this study in the corresponding part.

For AEs with completely missing or partially missing start dates, if there is no clear evidence that the AEs are pre-treatment or post-treatment, the AEs will be classified as TEAEs.

Details for imputing missing or partial start dates of adverse events are described in [Appendix C](#).

An overview of all TEAEs will be provided with the following categories separately for Parts A and B:

- Number of TEAEs (total number of TEAEs only)
- Subjects with any TEAEs
- Subjects with TEAEs by strongest relationship
- Subjects with TEAEs by maximum severity
- Subjects with TEAEs leading to study drug discontinuation (discontinuation of any study drugs)
- Subjects with TEAEs leading to study drug interruption (discontinuation of any study drugs)
- Subjects with Grade 3/4 TEAEs
- Subjects with related TEAEs
- Subjects with serious TEAEs
- Subjects with related serious TEAEs
- Subjects with TEAE leading to death

The frequency counts and percentages as well as the exposure adjusted event rate will be presented for the above overview table. The exposure adjusted rate will not be presented for strongest relationship and maximum severity categories.

The following summary tables of TEAEs will be presented separately for Parts A and B:

- All TEAEs
- Grade 3/4 TEAEs
- TEAEs by strongest relationship
- TEAEs by maximum severity
- TEAEs leading to treatment discontinuation
- TEAEs leading to treatment interruption
- Related TEAEs
- Serious TEAEs

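### Part B restarts the treatment-emergent clock on the same drug and dose, and no visible AE, exposure or threshold-event summary spans Parts A and B for rollover subjects

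*SAP*

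**What the plan says.** SAP 6.1 gives one regimen and dose for both parts. Subjects in Australia, Canada, Spain and Poland who complete Part A "would have the opportunity to participate in Part B for an additional 48 weeks". Protocol Synopsis and 9.3.2 put the main treatment period at up to 96 weeks.

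- **AE window.** The Part B treatment-emergent period in SAP 8.1 "will include the time from the first dose of study drug in Part B to 28 days after the last dose date" of Part B, or to completion of participation in Part B if earlier.
- **AE classes.** SAP 8.4.1 classes AEs by part. Pretreatment is "any AE that occurred before the first dose date of study drug in the TE Period in the corresponding part". A TEAE is one that worsened in severity or seriousness, or "newly developed at or after the first dose date of study drug in the TE Period in the corresponding part".
- **Baseline.** Except for sweat chloride, SAP 8.1 fixes it for both parts as the last value "collected before the first dose of ELX/TEZ/IVA in Part A of this study", and the Part B rows of Appendix A refer back to it.
- **Reporting.** SAP 3 states: "Analyses will be performed separately for Part A and B, unless otherwise specified". SAP 8.4 repeats this for safety ("Safety analysis will be summarized separately for Parts A and B") and SAP 8.2.5 for exposure ("Exposure summaries will be separated for Parts A and B based on the Safety Set"). The threshold counts in 8.4.2 to 8.4.4 are also taken within each part's own window.

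**The concern.** The sole objective is long-term safety and tolerability, and rollover subjects have the longest exposure in the study. For them, Part B Day 1 is an administrative boundary and not a first exposure. Calling an event that arose during up to 96 weeks on the same tablets pretreatment is correct by the part-specific definition but misleading to a reader of the Part B output.

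Three things are at stake:

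1. The Part B TEAE tables leave out on-drug events that persist unchanged, and they describe subjects selected for having completed Part A. A lower Part B incidence could be read as tolerability improving with time.
2. The simplest long-term question has no planned table: what proportion of subjects treated through both parts ever had a given event, and at what rate.
3. As the definitions read, an unchanged event from Part A that leads to stopping drug in Part B is not a Part B TEAE. It would be absent from the Part B table of TEAEs leading to discontinuation, while Part B disposition (SAP 8.2.1) reports the discontinuation and its reason.

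**Working it through.** **1. The plan's own figure.** SAP 6.2 says that with over 400 subjects and no events, a frequency above 1% is ruled out with 95% confidence. With n = 400, P(at least one event at 1%) = 1 − 0.99^400 = 98.2%. The one-sided 95% upper bound at 0/400 is 1 − 0.05^(1/400) = 0.75%. The statement holds for the enrolled total, and this point does not affect it.

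**2. Span.** 96 + 48 = 144 weeks at most. Part A is up to 96/144 = 67% of that time.

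**3. One subject through the planned outputs.** Suppose an ALT elevation is reported as an AE in Part A, persists through Part B and never worsens.

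| Output | Part A | Part B |
|---|---|---|
| TEAE tables (8.4.1) | counted | not counted: onset before first Part B dose, no worsening |
| AE listing (8.4.1) | listed | listed as pretreatment |
| Threshold counts (8.4.2) | counted if a threshold is met | counted again if a value in the Part B window still meets it |
| Change from baseline (8.4.2) | from the pre-Part A value | from the same value, so up to about 144 weeks |
| Exposure (8.2.5) | top category above 96 weeks | starts again at zero; top category above 48 weeks |

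The AE and threshold outputs use the same part-specific window. They differ because an AE is placed by onset or worsening, whereas a threshold event needs only a qualifying value in the window. No row gives a count or an exposure over both parts.

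**4. Can the cumulative figure be rebuilt from the two percentages?** For the same subjects, with pA and pB the proportions with the event in each part, the cumulative proportion lies between max(pA, pB) and pA + pB. For an illustration, assume a constant hazard, so pB = 1 − (1 − pA)^(48/96) and the 144-week value is 1 − (1 − pA)^(144/96).

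| pA (assumed) | pB | 144 weeks, constant hazard | Range without that assumption |
|---|---|---|---|
| 10.0% | 1 − 0.9^0.5 = 5.1% | 1 − 0.9^1.5 = 14.6% | 10.0% to 15.1% |
| 30.0% | 1 − 0.7^0.5 = 16.3% | 1 − 0.7^1.5 = 41.4% | 30.0% to 46.3% |

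Even these ranges need pA for the rollover subjects. The planned Part A tables use the whole Part A Safety Set, so they do not supply it. The same gap blocks a cumulative event rate, because the Part A events and exposure of rollover subjects are not tabulated separately.

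**5. Precision of a rollover-only table.** The documents do not give the size of Part B. If it is 50 to 200 (assumption), the zero-event upper bound 1 − 0.05^(1/n) runs from 5.8% down to 1.5%. At those sizes the 1% statement would not carry over to a 144-week table, which should not be presented as if it did.

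**The case against.** The strongest reply is that nothing is lost. Every event arising in Part A is a TEAE in tables that include all rollover subjects, and all AEs, including those classed as pretreatment, are listed. Worsened events and new episodes still count in Part B. Exposure-adjusted rates are planned for both parts, which deals with 96 against 48 weeks. A pre-drug reference value is the natural one for a change score. Protocol 9.3.2 regards up to 96 weeks as enough to evaluate long-term safety, and SAP 6.1 offers Part B to subjects in countries without commercial product.

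Absence also cannot be fully verified. The supplied protocol is the US version without Part B, the SAP contents list has a gap between 8.4.8 and 8.6, and SAP 3 allows exceptions to reporting by part.

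All of this stands and limits the point to what the visible summaries omit. It does not supply the missing result. Exposure adjustment corrects for length of follow-up, but not for selection of Part A completers or for persistent events that fall outside Part B. Listings allow reconstruction by hand, but they are not a planned summary.

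**Conclusion.** The point holds as a cheap improvement. Events that began on drug in Part A and continue unchanged are classed as pretreatment for Part B. Cumulative AE incidence, exposure and event rate over up to about 144 weeks cannot be derived from the visible planned summaries for rollover subjects.

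A reader might infer more than the documents support:

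- **That no table reaches 144 weeks.** The Part B Week 48 change-from-baseline tables do, because baseline precedes Part A.
- **That laboratory and vital-sign events run on a different clock from AEs.** Threshold events use the same part-specific window. Only the reference value is earlier.
- **That Part B tables hold only newly begun events.** Worsening also qualifies.
- **That 67% measures lost or misclassified events.** It is a ratio of maximum calendar lengths.

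The number of subjects affected is unknown, since Part B size is not given and only four countries take part. The percentages in the illustration rest on assumed incidences, and the 144-week values also on a constant hazard. Part A Week 96 and Part B Day 1 need not coincide, and time in another qualified study is excluded, so 144 weeks is a ceiling.

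**What to change.** 1. **SAP 8.1:** define a combined treatment-emergent period for the Part B Safety Set as the union of the Part A and Part B periods. It starts at the first Part A dose and excludes time in another Vertex study, as 8.1 already does by part. A union counts each day once and leaves out any gap between parts that lies in neither period.
2. **SAP 8.4.1:** over that period, add a cumulative TEAE summary consisting of the overview, SOC/PT, serious events, events leading to discontinuation, and the exposure-adjusted rate.
3. **SAP 8.2.5:** add a cumulative exposure summary for the same subjects, with categories that extend to the full span.
4. **Part B outputs:** flag events with on-drug onset in Part A as ongoing from Part A instead of pretreatment. Keep the existing pretreatment flag for AEs that began in another qualified Vertex study and are ongoing at the Returning Visit.

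The cost is SAP wording and one extra set of tables from data already collected, with no effect on sample size or error rates. Rollover subjects' Part A events will also appear in the Part A tables, so the cumulative tables need a footnote that they are not additive to those.

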### 9.7 Dose Modification for Toxicity

No dose modifications for toxicity are allowed. Treatment may be interrupted as outlined in Section 9.8. If any unacceptable toxicity arises, individual subjects will discontinue dosing (Section 9.9).

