### 12.3.3.1 Adverse Events

For analysis purposes, AEs will be classified as pretreatment AEs, TEAEs, or post-treatment AEs, defined as follows:

- **Pretreatment AE:** any AE that occurred before the first dose of study drug in the TE Period in this study
- **TEAE:** any AE that worsened (either in severity or seriousness) or newly developed at or after the first dose date of study drug in the TE Period in this study
- **Post-treatment AE:** any AE that worsened (either in severity or seriousness) or newly developed after the TE Period in this study

For AEs with missing or partial start dates, if there is no clear evidence that the AEs started before or after study drug treatment, then the AEs will be classified as TEAEs.

AE summary tables will be presented for TEAEs only and will include the following:

- All TEAEs
- TEAEs by strongest relationship
- TEAEs by maximum severity
- TEAEs leading to treatment discontinuation
- TEAEs leading to treatment interruption
  - Serious TEAEs
  - TEAEs leading to death
  - Grade 3 and Grade 4 TEAEs
  - Frequently reported TEAEs

Summaries will be presented by MedDRA SOC and PT using frequency counts and percentages (i.e., number and percentage of subjects with an event). When summarizing the number and percentage of subjects with an event, subjects with multiple occurrences of the same AE or a continuing AE will be counted once, only the maximum severity level will be presented in the severity summaries, and the strongest relationship level will be presented in the relationship summaries. An AE overview table will be provided. In addition, a listing containing individual

subject level AE data for all deaths and other serious and significant AEs will be provided separately. All AEs, including pre- and post-treatment AEs, will be presented in individual subject data listings.

Exposure-adjusted event rates may also be provided.

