**Table 13-3 Classifications for Study Drug Action Taken With Regard to an AE**

Classification	Definition
Dose not changed	Study drug dose not changed in response to an AE
Dose reduced	Study drug dose reduced in response to an AE
Drug interrupted	Study drug administration interrupted in response to an AE
Drug withdrawn	Study drug administration permanently discontinued in response to an AE
Not applicable	Action taken regarding study drug administration does not apply. "Not applicable" will be used in circumstances such as when the investigational treatment had been completed before the AE began and no opportunity to decide whether to continue, interrupt, or withdraw treatment is possible.

AE: adverse event

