- Related serious TEAEs

- TEAEs leading to death

Summaries will be presented separately for Parts A and B by MedDRA SOC and PT using frequency counts and percentages (i.e., number and percentage of subjects with an event) and the exposure adjusted event rate (except for summary by strongest relationship and maximum severity). When summarizing the number and percentages of subjects, subjects with multiple occurrences of the same adverse event or a continuing adverse event will be counted once, and only the maximum severity level will be presented in the severity summaries, and the strongest relationship level in the relationship summaries.

Additional summary tables separately for Parts A and B will be presented for TEAEs showing number, percentage of subjects, and the exposure adjusted event rate

- All TEAEs by PT

All AEs, including pretreatment AEs, TEAEs, and post-treatment AEs, will be presented in an individual subject data listing based on the All Subjects Set separately for Parts A and B. In addition, a listing containing individual subject adverse event data for TEAEs leading to treatment discontinuation, TEAEs leading to treatment interruption, Grade 3/4 TEAEs, SAEs and all deaths will be provided, with a flag indicating the TEAE status for SAEs and deaths for Parts A and B separately.

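### Does the SAP's overview row for TEAEs leading to study drug interruption really count discontinuations?

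*SAP*

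**What the plan says.** SAP 8.4.1 lists the rows of the TEAE overview, to be produced separately for Parts A and B. Two adjacent rows concern action on study drug. The upper one reads "Subjects with TEAEs leading to study drug discontinuation (discontinuation of any study drugs". The lower one differs from it by a single word, in the label and not in the bracket: "Subjects with TEAEs leading to study drug interruption (discontinuation of any study drugs".

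In each case the bracket closes after the last word shown. On the statistics, the section states: "The frequency counts and percentages as well as the exposure adjusted event rate will be presented for the above overview table". It then exempts only the strongest-relationship and maximum-severity rows from the rate, so the interruption row receives a count, a percentage and a rate.

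The same section goes on to plan separate summary tables by system organ class and preferred term for discontinuation and for interruption, with no bracketed gloss on either. It also plans a subject listing in which "TEAEs leading to treatment discontinuation, TEAEs leading to treatment interruption, Grade 3/4 TEAEs, SAEs and all deaths will be provided". Protocol 12.3.3.1 likewise gives "TEAEs leading to treatment interruption" its own line, next to the one for discontinuation.

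**The concern.** The bracket contradicts the label beside it. A gloss of this kind normally tells the programmer how to build the row, and this one says discontinuation. Followed literally, the interruption row would reproduce the row above and could then disagree with the plan's own interruption table and listing.

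The row is not redundant in this trial. Protocol 9.7 says: "No dose modifications for toxicity are allowed. Treatment may be interrupted as outlined in Section 9.8". With dose modification for toxicity ruled out, interruption is the recorded response short of stopping, so it carries tolerability information that discontinuation does not. TEAEs belong to the primary safety and tolerability endpoint, and the overview is the first AE table many readers will look at. Two rows that were the same by construction would hide every subject whose drug was paused and later resumed.

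**Working it through.** The plan states no figure to reproduce here. The check is a comparison of texts, followed by a count of what the phrase could touch.

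**1. How the documents treat the two actions**

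| Place | Discontinuation | Interruption |
|---|---|---|
| SAP 8.4.1, overview label | own row | own row |
| SAP 8.4.1, overview bracket | discontinuation | discontinuation (the slip) |
| SAP 8.4.1, tables by class and term | own table | own table |
| SAP 8.4.1, subject listing | named | named separately |
| Protocol 12.3.3.1, AE summaries | own line | own line |
| Protocol Table 13-3, action taken | "Study drug administration permanently discontinued in response to an AE" | "Study drug administration interrupted in response to an AE" |
| Protocol 9.8.1, liver function tests | own criterion | own criteria, with resumption possible in some cases |

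Only one cell is out of line. No passage says that an interruption is to be counted as a discontinuation.

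**2. What the bracket is for**

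Protocol Section 10 defines study drug as two products, the triple-combination tablet and the ivacaftor tablet. The working part of both brackets is therefore the reference to any study drug: action on either product is enough for the event to count. SAP 8.2.6 applies the same any-drug rule to interruption when it defines compliance. The any-drug rule survives the wrong noun, and the natural explanation is that the bracket was copied down from the row above.

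**3. Where the data come from**

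The row is built from the action-taken classification recorded for each AE. Table 13-3 has distinct values for drug interrupted and drug withdrawn, so a programmer selecting records for a row labelled interruption has one obvious value to select.

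**4. Scope if the bracket were followed**

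- The overview has 11 categories: number of TEAEs, any, strongest relationship, maximum severity, discontinuation, interruption, Grade 3/4, related, serious, related serious, and death. One of the 11 is affected.
- Figures affected: 3 statistics × 2 parts = 6.
- Error in the subject count, per part = (subjects with a TEAE leading to interruption) − (subjects with a TEAE leading to discontinuation). Neither number is in the documents, and the difference could be zero.
- Error in the exposure-adjusted rate, per part = (interruption events − discontinuation events) ÷ the exposure used as denominator. This cannot be evaluated either.
- Weight of one subject in Part A: SAP 6.2 says more than 400 subjects were enrolled. Assuming that at least 400 were dosed, one subject is at most 100/400 = 0.25 percentage points. The size of Part B is not given.

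**5. Scope if the label is followed**

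All 6 figures are correct and the error is zero.

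**The case for a change.** The strongest case for a change is that a SAP should specify its outputs without leaving the reader to decide which half of a line to ignore. The wording is current, complete and wrong, and nothing elsewhere corrects the phrase itself. The repair would be a few words, and SAP Section 3 provides the route: an amendment before database lock, or a note in the clinical study report afterwards. Merely ignoring the bracket would also leave the any-drug rule for this row to inference.

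The textual fact stands in full, and the correction would do no harm. What does not stand is any consequence. To go wrong, a programmer would have to set aside the row label, the companion table, the listing and the action-taken field in favour of three or four bracketed words. If that happened, the overview would show two adjacent rows with identical counts and rates beside an interruption table that would normally differ, a mismatch that routine output checks should catch. The any-drug rule is not lost either: it can still be read from the bracket, and SAP 8.2.6 states it for interruption in the compliance setting. Even if the row were wrong, the full interruption data would remain in the table by class and term and in the subject listing, neither of which carries the faulty gloss.

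**Conclusion.** The bracket on the interruption row is wrong, almost certainly copied from the row above, and no change to the plan follows. The rest of the SAP and the protocol fix the intended meaning, and the recorded data already separate the two actions, so a competent analyst will program the row as labelled. The expected effect on the results is nil. The outer limit is 6 descriptive figures in 1 of 11 overview categories, by an amount the documents do not allow anyone to calculate.

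This rests on two assumptions: that the analyst follows the label where label and bracket conflict, and that the case report form records action taken in the categories of Table 13-3. SAP 8.4 limits the safety analysis to description without testing, so no error rate or power is involved, and neither document attaches a decision to this row.
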